### **2.3.3 Primary endpoint**

The primary objective of the trial was to demonstrate that an immunosuppressive regimen based on everolimus (EVR) in co-exposure with tacrolimus (TAC) has superior efficacy compared to tacrolimus alone on estimated glomerular filtration rate (MDRD-4 formula) at 12 months after transplantation in de novo liver transplant recipients.

The primary efficacy variable of this trial is the renal function at Month 12 after baseline assessed by estimated GFR based on recalculated values according to the MDRD-4 formula:

$$\text{eGFR [mL/min/1.73m}^2\text{]} = \text{eGFR} = 186.3 * C^{-1.154} * A^{-0.203} * G * R,$$

where C is the serum concentration of creatinine [mg/dL], A is age (years), G=0.742 when gender is female, otherwise G=1, R=1.21 when race is black, otherwise R=1.

### **2.3.4 Statistical hypothesis, model, and method of analysis**

The trial tests the null hypothesis that the treatment difference (investigational minus control) in mean eGFR at Month 12 after baseline is zero versus the alternative hypothesis that the treatment difference was different from zero.

The hypotheses was tested with an analysis of covariance (ANCOVA) with treatment , center, HCV-Class (positive, negative) and lab MELD ( $\leq 30$  vs  $> 30$ ) as factors, and eGFR at Visit 2 (Baseline) as covariate. Raw as well as adjusted means (= LS-means, LS: least square means) were presented for the treatment contrast together with a two-sided p value and the appropriate confidence interval, respectively. The significance level was 5% (two-sided). There are no multiplicity issues to be addressed since only the hypothesis of superior efficacy of the investigational vs. the control regimen was tested confirmatorily.

The Full Analysis Set was used for the primary analysis. Patients will be analyzed in their randomized group.

### **2.3.5 Handling of missing values/censoring/discontinuations**

Missing values in eGFR will be imputed with the last valid observed value from that patient (LOCF). Under the assumption that the eGFR will remain fairly stable in the control group but will probably improve in the investigational group, this strategy corresponds to a conservative estimate of the treatment effect.

As sensitivity analyses a multiple imputation (Molenberghs & Kenward 2007; White, Royston & Wood 2010) will be performed. The specification for the multiple imputation procedure are presented in appendix 5.5.2.

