#### 10.4.4 Supportive analyses

For sensitivity, the following analyses will be performed:

The primary analysis will be repeated with the Per-protocol Set using the same ANCOVA model as described above.

As a further supportive analysis, a Mixed Model for Repeated Measures (MMRM) will be fitted using treatment group, visit (as a categorical time variable) and subject as categorical variables ([Molenberghs & Kenward 2007](#)). Assuming that the time profile is not the same in the two treatment groups, a full visit-by-treatment interaction will be used. If a baseline is to be included in the model, the baseline-by-time interaction will be included in the model, otherwise strange and unrealistic restrictions on the implied covariance structure would be made in this case. An unstructured covariance matrix will be used. Since there are sufficient data, using a different covariance matrix in each treatment group might be considered:

```
proc mixed;
class subject visit treatment;
model gfr = baseline treatment visit baseline*visit treatment*visit / s ddfm=kr;
repeated time / subject = subject type = un group=treatment;
run;
```

The estimated adjusted treatment effect as well as the treatment contrast will be presented for the Month 12 visit together with appropriate two-sided 95% confidence intervals. The model will be fitted for both, the FAS as well as the PP set.

Only in case of substantial drop-out (>20%) or if relevant differences in the drop-out-patterns between the two treatment groups are observed, a multiple imputation of missing values ([Molenberghs & Kenward 2007](#); [White, Royston & Wood 2010](#)) will be performed as an alternative to account for missing values. The necessity of this procedure will be decided during the data review meeting, computational details (e.g. seed value, method for imputation) will be described in the statistical analysis plan to be finalized before database lock.

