### Document History – Changes compared to previous final version of SAP

Date	Time point	Reason for update	Outcome for update	Section and title impacted (Current)
06NOV2017	Prior to - DB lock		N/A - First version	NA

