### **2.3.6 Supportive analyses**

For sensitivity, the following analyses will be performed:

The primary analysis will be repeated with the Per-protocol Set using the same ANCOVA model as described above.

As a further supportive analysis, a Mixed Model for Repeated Measures (MMRM) will be fitted using treatment group, visit (as a categorical time variable) and subject as categorical variables (Molenberghs & Kenward 2007). Assuming that the time profile is not the same in the two treatment groups, a full visit-by-treatment interaction will be used. Baseline and the baseline-by-time interaction will be included in the model. An unstructured covariance matrix will be used.

The estimated adjusted treatment effect as well as the treatment contrast will be presented for the Month 12 visit together with appropriate two-sided 95% confidence intervals. The model will be fitted for the FAS.

Because there are less than 20 % study discontinuations in the study no multiple imputation of missing values (Molenberghs & Kenward 2007; White, Royston & Wood 2010) was performed as an alternative to account for missing values.

The course of eGFR was summarized descriptively by visit and treatment group for the FAS. Absolute and percent changes from baseline to each post-baseline measure were calculated by

treatment group for each study visit as post-baseline minus baseline value. Between-group as well as within-group comparisons will be performed exploratory using suitable parametric (t-test/paired t-test).

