### 5.5.2 Key secondary analysis

*Multiple imputation (Molenberghs & Kenward 2007; White, Royston & Wood 2010)*

Alternative to LOCF, additionally as sensitivity analyses a multiple imputation (Molenberghs & Kenward 2007; White, Royston & Wood 2010) is planned:

\* Impute values via MCMC to obtain a monotone missing pattern\*;

```

proc mi data=&data out=gfr_mono n impute=20 seed=579415 NOPRINT
  by tgplc;
  mcmc chain=multiple impute=monotone;
  var v:;
run;

** Impute values via predictive mean matching *;
proc mi data=gfr_mono out=gfr_imp n impute=1 seed=579214 NOPRINT;
  by tgplc _imputation_;
  monotone regpmm;
  var v:;
run;

ods output LSMeans=LSMeans; *** LsMeans+CL for effects ***;
ods output Estimates=gfr_imp; *LsMeans+CL for contrasts;
proc glm data=gfr_imp;
  by _imputation_;
  class tgplc ctr1n;
  model egfr_im = baseline tgplc HCV_class lab_MELD_class / ss3;
  lsmeans tgplc / stderr ;
  estimate "mean difference" tgplc 1 -1;
run;
quit;

*lsmeans;
proc sort data=LSMeans;
  by tgplc;
run;

ods listing close;
ods rtf exclude all;
ods output ParameterEstimates=LSMeanMI;
proc mianalyze data=LSMeans;
  by tgplc;
  modeleffects lsmean;
  stderr stderr;
run;
*lsmean difference;
proc sort data=LSMeanDiff;
  by parameter;
run;

ods output ParameterEstimates=LSMeanDiffMI;
proc mianalyze data=LSMeanDiff;
  by parameter;
  modeleffects estimate;
  stderr stderr;
run;

```

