## NOTE TO FILE

Subject: Statistical Analysis Plan (SAP) vs. Analysis

Issue:

Although no multiple analysis is planned in the statistical analysis plan (version 1.0, dated 06NOV2017), it was nevertheless included in the planning of the mock tables (RAP Module 6 - Text tables and figure, version 1.0, dated 21MAR2018). Accordingly, the multiple imputation was programmed and reported.

Authorization:

Name, Function:

Date, signature:

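### The SAP plans multiple imputation, then says it was not done, and a note to file calls it unplanned but reported; the printed listings do not implement the stated MI, MMRM or primary ANCOVA

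*SAP*

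**What the plan says.** The primary analysis is an ANCOVA of Month 12 eGFR with LOCF (SAP 2.3.4, 2.3.5 and 5.2). Three statements follow on MI.

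- **Planned.** SAP 2.3.5 says MI will be done as a sensitivity analysis: "The specification for the multiple imputation procedure are presented in appendix 5.5.2". Section 5.5.2 agrees ("Alternative to LOCF, additionally as sensitivity analyses a multiple imputation") and prints code with 20 imputations and two seeds. The only SAP version is dated 06NOV2017, with the time point "Prior to - DB lock".
- **Not performed.** SAP 2.3.6: "Because there are less than 20 % study discontinuations in the study no multiple imputation of missing values" was carried out.
- **Unplanned, but reported.** The note to file: "Although no multiple analysis is planned in the statistical analysis plan", it entered the mock tables ("version 1.0, dated 21MAR2018"). It ends: "Accordingly, the multiple imputation was programmed and reported".

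Protocol 10.4.4 makes MI conditional on drop-out above 20%, "or if relevant differences in the drop-out-patterns between the two treatment groups are observed", and leaves the decision to the data review meeting.

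SAP 2.3.6 also plans an MMRM on the full analysis set, with no condition attached. SAP 2.3.4 names centre as a factor in the primary ANCOVA. Section 4 lists the changes in statistical methods from the protocol.

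**The concern.** The LOCF ANCOVA carries the only confirmatory claim, and MI and MMRM are the analyses that test how far it depends on carrying values forward. A reader needs to know which of these were committed to, under what rule, and what model was fitted.

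On MI the documents give three answers that cannot all be true, and 2.3.6 applies only half of the protocol's rule. The code in 5.5.1 and 5.5.2 is the most precise statement of the models in the SAP, and it departs from the text at points that decide what is estimated. For the sensitivity analyses, this means the promised treatment difference at Month 12 cannot be obtained from the printed code. For the primary analysis, it leaves open whether centre was in the model.

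**Working it through.** **1. Status of MI.** SAP 2.3.5 and 5.5.2 commit to MI without condition. SAP 2.3.6 applies a condition and reports the outcome as no MI. The note to file denies the commitment in 2.3.5 and contradicts the outcome in 2.3.6. The note says multiple analysis, but its last sentence shows that imputation is meant. Section 4 does not declare unconditional MI as a departure from Protocol 10.4.4.

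**2. The second trigger.** An overall rate below 20% cannot answer it. With 165 per arm, 50 of 330 missing is 15%. That may be 25 vs 25 (15% each) or 33 vs 17 (20% vs 10%). Study discontinuation is also not the same quantity as a missing Month 12 eGFR, which is what LOCF fills in.

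**3. The listings, read statement by statement.**

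| Listing | As printed | Consequence |
|---|---|---|
| MI (5.5.2) | `Estimates` are written to `gfr_imp`, the data set GLM is reading | Output and input share a name |
| MI (5.5.2) | `LSMeanDiff` is sorted and passed to MIANALYZE, but no step creates it | Treatment difference is not pooled |
| MI (5.5.2) | GLM runs BY `_imputation_` on data ordered by `tgplc` first | BY order is wrong; a sort is missing |
| MMRM (5.5.2) | REPEATED uses `time`, which is not in CLASS (also so in the protocol's code) | Visit structure is not specified |
| MMRM (5.5.2) | `tgplc` in MODEL, `treatment` in CLASS and GROUP | Two names for one factor |
| MMRM (5.5.2) | No LSMEANS or ESTIMATE statement | The Month 12 contrast promised in 2.3.6 is not requested |
| Primary GLM (5.5.1) and MI GLM (5.5.2) | Centre in CLASS, absent from MODEL | Not the ANCOVA of 2.3.4 |

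**4. Changes missing from Section 4.** Protocol 10.5.1 handles missing secondary eGFR values by MI; SAP 2.5.3 uses LOCF. Protocol 10.4.4 fits the MMRM to the full analysis set and the per-protocol set; SAP 2.3.6 keeps only the first. Section 4 mentions neither.

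**5. What LOCF could do (illustration).** Inputs from the sample size sections: SD 18.0 and 165 per arm. The plan's own figure reproduces: a two-sample t-test for a difference of 7.0 needs 105 per group (power 0.801), and 105/0.8² = 164.06, so 165.

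Assumed, because the documents give no values: 20% of Month 12 values missing on everolimus and 10% on control, a mean fall of 10 mL/min/1.73m² in both arms, no true effect, and drop-out spread evenly over the year. Let f be the share of the fall that comes after the last value.

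- Bias = f × (0.20 × 10 − 0.10 × 10) = f × 1.0, in favour of everolimus.
- SE = 18 × √(2/165) = 1.98.
- Two-sided type I error = Φ(−1.96 + bias/SE) + Φ(−1.96 − bias/SE).

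For a fall starting at day 90 and no Visit 9a, half the drop-outs have a last value at or before day 90, a quarter at day 180 and a quarter at day 270. So f = 0.5 × 1 + 0.25 × 180/270 + 0.25 × 90/270 = 0.75. The other rows follow in the same way from the visit days.

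| Fall starts | Visit 9a at drop-out | f | Bias | Type I error |
|---|---|---|---|---|
| Day 90 | No | 0.75 | +0.75 | 6.7% |
| Day 1 | No | 0.61 | +0.61 | 6.1% |
| Day 90 | Yes | 0.62 | +0.62 | 6.1% |
| Day 1 | Yes | 0.50 | +0.50 | 5.7% |

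Simulated ANCOVAs for the two rows without Visit 9a (assumed baseline to Month 12 correlation 0.45) also gave 6.7% and 6.1%. With 15% missing in each arm the bias is zero.

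Under the SAP's own assumption (control stable, everolimus improving, here by 7 after the last value) the shift is −7 × 0.10, −7 × 0.15 or −7 × 0.20, that is −0.7, −1.05 or −1.4. LOCF is then conservative, as the SAP says.

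**The case against.** The other side has several good points.

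- **Timing.** Mock tables dated 21MAR2018 come 135 days after the SAP, and a reader might infer that MI was chosen once results were visible. The documents do not support that. The method, the number of imputations and both seeds stand in the SAP dated before database lock; the later date concerns table planning, and no lock date is given. Only whether MI would be run is unclear.
- **MI as the sole check.** It is not. The MMRM carries nothing forward and is planned unconditionally. This stands, although its listing is faulty too.
- **Second trigger.** Its only consequence would be to run MI, and MI was run. The data review minutes, which are not in the documents, may also cover it. Nothing shows that drop-out patterns differed. What stands is that 2.3.6 gives a reason for not doing MI that does not meet the protocol's rule.
- **Bias.** Study-drug discontinuation is not study withdrawal, Month 12 eGFR is required afterwards (Protocol 6.6.3, 6.6.8 and Section 7), and SAP 5.2 puts Visit 9a in the LOCF sequence. A type I error of 8.0% would need f = 1, with every last value at or before day 90. The smaller range is the fair one, and even that rests on assumed missing shares.
- **Listings.** They are excerpts, and the programs that were run may differ. A two-level `tgplc` outside CLASS gives an equivalent fixed effect if it is numeric. The underived `egfr_im` and possible PDF artefacts are not relied on here. The missing data set, the reused name, the missing sort, `repeated time` and the missing centre term cannot be explained that way.

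**Conclusion.** The point holds as a contradiction in the plan and a mismatch between text and code. MI was prespecified as a method, but the SAP and its note to file disagree on whether it was to be done. The printed MI code gives no pooled difference, the printed MMRM code gives no Month 12 contrast, and two protocol changes are undeclared.

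The most consequential item is centre. If 5.5.1 was run as printed, the confirmatory estimate came from a model other than the one in 2.3.4. The size of that difference cannot be derived from the documents.

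A reader might go further and conclude that LOCF favoured everolimus, or that the reported results are wrong. Neither follows. The documents give no missing shares or eGFR falls by arm, so 5.7% to 6.7% is conditional on the assumptions above. Bias vanishes at equal missingness with equal falls and reverses under the SAP's own assumption. The listings show what was printed, not what was executed.

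**What to change.** Keep LOCF ANCOVA as the primary analysis, and make these changes:

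- **5.5.1 and the MI GLM in 5.5.2:** put centre in MODEL so that both match 2.3.4. State that this can change the primary estimate if the printed code was the code used.
- **2.3.6:** replace the paragraph on the 20% threshold with: *MI (5.5.2) is a sensitivity analysis reported beside the MMRM.* Declare this in Section 4 as a departure from the protocol's conditional rule, and correct the note to file to agree.
- **MI listing:** sort by `_imputation_` before GLM and write `Estimates` to `LSMeanDiff`.
- **MMRM listing:** use `repeated visit`, one treatment variable name in CLASS, MODEL and GROUP, and an explicit Month 12 contrast.
- **Section 4:** list the move of secondary eGFR from MI to LOCF and the loss of the per-protocol MMRM, or restore both analyses.

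A table by arm of observed and carried-forward Month 12 values would help the reader, but it is a reporting preference.

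Cost: SAP text, listing corrections and a little more programming and reporting; the note to file says MI has already been programmed. No new data are needed, and sample size and alpha do not change. MI and MMRM both rest on missing-at-random, so they complement LOCF rather than settle the question.

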### **2.3.6 Supportive analyses**

For sensitivity, the following analyses will be performed:

The primary analysis will be repeated with the Per-protocol Set using the same ANCOVA model as described above.

As a further supportive analysis, a Mixed Model for Repeated Measures (MMRM) will be fitted using treatment group, visit (as a categorical time variable) and subject as categorical variables (Molenberghs & Kenward 2007). Assuming that the time profile is not the same in the two treatment groups, a full visit-by-treatment interaction will be used. Baseline and the baseline-by-time interaction will be included in the model. An unstructured covariance matrix will be used.

The estimated adjusted treatment effect as well as the treatment contrast will be presented for the Month 12 visit together with appropriate two-sided 95% confidence intervals. The model will be fitted for the FAS.

Because there are less than 20 % study discontinuations in the study no multiple imputation of missing values (Molenberghs & Kenward 2007; White, Royston & Wood 2010) was performed as an alternative to account for missing values.

The course of eGFR was summarized descriptively by visit and treatment group for the FAS. Absolute and percent changes from baseline to each post-baseline measure were calculated by

treatment group for each study visit as post-baseline minus baseline value. Between-group as well as within-group comparisons will be performed exploratory using suitable parametric (t-test/paired t-test).

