## **11 Discussion and rationale for study design features**

The evaluation of the efficacy and safety of an immunosuppressive regimen in liver transplant recipients is best investigated using a randomized control trial, as opposed to observational studies where confounding by indication cannot be fully accounted for by adjusting by multivariate procedures for differences in confounders that are imbalanced at the time of transplantation. This protocol will not utilize procedures to blind investigators or subjects to treatment assignment. The duration of experience of liver transplant physicians with tacrolimus indicates that optimizing the safety of this medication requires the physician to be aware of the use of tacrolimus and to the trough levels. This open label study, however, does include prospective collection of assessments that relate to potential issues that may be impacted by an open label design, e.g. management of tacrolimus levels above or below target ranges. Importantly, the occurrence of the primary endpoints of this study are objectively measured – renal function by laboratory data, and death or graft survival.

The choice of the control arm for this study is based upon the predominance of tacrolimus use in liver transplantation worldwide in combination with corticosteroids, which are eliminated sometime after the first several months post-transplantation. As opposed to renal transplantation where triple or quadruple therapy is standard, adjunctive therapy with MMF is not pervasive and tends to be used short-term to allow a slow increase in the tacrolimus level while renal function recovers. The present study requires the discontinuation of MMF prior to randomization so that the control group is reflective of a regimen that has an approved liver transplant indication.

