### 1.1 Study design

This study was designed to provide data on efficacy and safety of a post-transplantation regimen in liver allograft patients consisting of reduced tacrolimus in the presence of everolimus.

This is a 12-month, multi-center, open-label, randomized, controlled study to evaluate efficacy and safety and evolution of renal function of everolimus (EVR) in co-exposure with tacrolimus (TAC) in de novo liver transplant recipients.

The trial tests the null hypothesis that there was no difference in renal function, estimated by eGFR according to the MDRD-4 formula, at 12 months after randomization between the everolimus-based tacrolimus-minimization regimen and the tacrolimus-based control regimen versus the alternative hypothesis that the difference is 7.0 ml/min/1.73m^2. A sample size of 105 in each group has 80% power to detect a difference in means of 7.0 ml/min/1.73m^2 assuming that the common standard deviation was 18.0 ml/min/1.73m^2 with a 5% two-sided significance level. (One will decide in favor of H1 when the difference in means would be 5.1 ml/min/1.73m^2 or greater in favor of the everolimus-based group.) To adjust the sample size for a common drop-out rate (DOR) of 20% (using the formula Nadj=N/(1-DOR)), 165 patients need to be randomized per group. Sample sizes were estimated using NQuery (Version 6.1) procedure “Two-group t-test for equal means (equal n’s)”.

At Baseline (Visit 2) between 7 and 21 days post LTx patients were assigned to one of the following two treatment groups in a ratio of 1:1.

- EVR/TAC group (ARM I):  
Everolimus (C0-h: 3-8 ng/mL\*) + tacrolimus (C0-h: < 5 ng/mL\*)
- TAC group (ARM II):  
Tacrolimus (C0-h: 6-10 ng/ml\*)

\*Trough levels as per local practice, e.g. liquid chromatography coupled with mass spectrometry (LCMS). Values derived from enzyme based assays were corrected (as described in the manufacturer's instructions).

No interim analysis was planned and performed.

An independent Data Safety Monitoring Board (DSMB) was instituted before study start. The DSMB reviewed safety-related issues in a meeting and were entitled to make recommendations for changes in study conduct. Details on the function of the DSMB and the frequency of the DSMB meetings was laid out in a separate DSMB Charter.

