## 1.3 Study objectives and endpoints

The primary objective was to demonstrate that an immunosuppressive regimen based on everolimus (EVR) in co-exposure with tacrolimus (TAC) has superior efficacy compared to tacrolimus alone on estimated glomerular filtration rate (MDRD-4 formula) at Month 12 in de novo liver transplant recipients.

The key secondary objective was to evaluate the incidence of a composite of treated biopsy proven acute rejection (BPAR), graft loss or death until Month 12.

Other efficacy related secondary objectives were

- To evaluate the incidence of a composite of treated BPAR, graft loss, death or loss to follow-up at months 6 and 12.
- To evaluate the incidence of each component of the composite efficacy endpoint at month at months 6 and 12.
- To evaluate the incidence of a composite of death or graft loss at months 6 and 12.
- To evaluate treated BPAR by: (1) incidence, (2) time to event, (3) severity, (4) final clinical diagnosis and outcome.
- To evaluate any acute rejection by: (1) incidence, (2) time to event, (3) severity(4) final clinical outcome outcome.
- To evaluate the incidence of:
  - Treated acute rejection.
  - BPAR.

- Treated BPAR

Other renal function related related secondary objectives were

- To evaluate the evolution of post-randomization renal function over time assessed by the change in estimated GFR (MDRD-4), including to Months 6, and 12.
- To evaluate renal function by eGFR using various methods (MDRD-4, Nankivell, Cockcroft-Gault, CKD-EPI and Hoek formulae).
- To evaluate the incidence of patients experiencing a decline in eGFR (MDRD-4) of < 10, 10<15, 15<20, 20<25, and  $\geq$  25 mL/min/1.73m^2 from Screening, Week 2 post transplantation (Day 15) and randomization to Months 6, and 12.
- To evaluate serum creatinine at various time points.
- To evaluate renal function and change in eGFR from screening, randomization, and Week 2 post transplantation (Day 15) to Months 6 and 12 eGFR in following subgroups: age (< 60 and  $\geq$  60 years), gender, race, renal function strata (< 30, 30<45, 45<60,  $\geq$  60 mL/min/1.73m^2, below/above 45 mL/min/1.73m^2, below/above 60 mL/min/1.73m^2), HCV status, lab MELD score categories ( $\leq$ 14, 15-19, 20-24, 25-29,  $\geq$  30), and diagnosis leading to transplantation.
- To evaluate urinary protein/creatinine ratio at various time points.
- To evaluate the incidence of proteinuria. as adverse event of special interest.

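### Between Month 12 and Month 6, and before Month 6, the eGFR course is compared between arms only by unadjusted t-tests, although the planned MMRM could give a baseline-adjusted contrast at every visit

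*SAP*

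**What the plan says.** SAP 1.3 lists a secondary objective: "To evaluate the evolution of post-randomization renal function over time assessed by the change in estimated GFR (MDRD-4), including to Months 6, and 12". SAP 2.3.6 serves it with by-visit summaries on the FAS. "Absolute and percent changes from baseline to each post-baseline measure were calculated by" treatment group and visit, and the next sentence reads: "Between-group as well as within-group comparisons will be performed exploratory using suitable parametric (t-test/paired t-test". That sentence does not name its variable. Change from baseline is the natural reading, because the sentence before it defines change. Protocol 10.4.4 has the same t-tests, with rank tests beside them.

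Baseline is Visit 2: "At Baseline (Visit 2) between 7 and 21 days post LTx".

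Two baseline-adjusted models are already planned:

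- The primary ANCOVA at Month 12 (SAP 2.3.4) has "eGFR at Visit 2 (Baseline) as covariate". SAP 2.5.2 repeats this model at Month 6 and says expressly that MDRD-4 is included there.
- The supportive MMRM (SAP 2.3.6 and 5.5.2): "Baseline and the baseline-by-time interaction will be included in the model", and "a full visit-by-treatment interaction will be used". Its treatment contrast with 95% CI is promised for Month 12 only.

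The post-baseline visits are Days 8 and 15 and Months 1, 3, 6, 9 and 12 (Protocol section 4 and the assessment schedule in section 7).

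**The concern.** Taking the adjusted analyses out of the visit list leaves Days 8 and 15 and Months 1, 3 and 9. There, the only clearly planned between-arm comparison of the primary variable ignores baseline except by subtracting it. Subtraction fixes the slope on baseline at 1. If the true slope differs, the comparison is noisier than it need be, and a chance difference in baseline eGFR passes partly into the estimated arm difference.

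These visits show when a renal difference appears and whether it lasts. Protocol section 4 expects the reduced tacrolimus target in Arm 1 by three weeks after randomization, so Months 1 and 3 are where a difference could first be seen. At Months 6 and 12 the t-test adds a second, unadjusted p-value beside the ANCOVA, and the SAP does not say which is to be read if they differ.

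**Working it through.** **Inputs from the documents.** SD 18.0, difference 7.0 mL/min/1.73m², two-sided 5%, 105 per arm, 20% drop-out, 1:1 allocation (SAP section 3 and 1.1).

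**The plan's own figure.** The exact two-sample t-test has 79.7% power at 104 per arm and 80.1% at 105, so 105 reproduces. Drop-out: 105 / 0.8² = 164.06, rounded up to 165.

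**Assumptions, not in the documents.** r = correlation of baseline with follow-up eGFR; k = baseline SD / follow-up SD. The SD of 18 is a Month 12 planning value and is used here for all visits.

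**Precision.** With n per arm and follow-up SD s:

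- change score: variance = (2/n) · s² · (1 + k² − 2rk)
- baseline-adjusted: variance = (2/n) · s² · (1 − r²)
- ratio = 1 + (k − r)² / (1 − r²)

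The ratio is never below 1. It equals 1 only if k = r, that is, if the slope on baseline (r/k) is 1. The degree of freedom spent on the slope is negligible at this sample size.

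| k | r | Variance ratio | SE excess |
|---|---|---|---|
| 0.8 | 0.7 | 1.02 | 1% |
| 0.8 | 0.5 | 1.12 | 6% |
| 0.8 | 0.3 | 1.27 | 13% |
| 1 | 0.9 | 1.05 | 3% |
| 1 | 0.8 | 1.11 | 5% |
| 1 | 0.7 | 1.18 | 8% |
| 1 | 0.5 | 1.33 | 15% |
| 1 | 0.3 | 1.54 | 24% |
| 1.33 | 0.6 | 1.84 | 36% |
| 1.33 | 0.4 | 2.04 | 43% |
| 1.33 | 0.2 | 2.34 | 53% |

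Worked example, k = 24/18 = 1.33, r = 0.2: 1 + (1.133)² / 0.96 = 1 + 1.284 / 0.96 = 2.34, square root 1.53. The 53% is not a ceiling: k = 1.5 with r = 0.3 gives a ratio of 2.58, an SE excess of 61%.

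**What that means at 105 per arm, k = 1, true difference 7.0** (an illustration, since 7.0 is the Month 12 planning value):

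| r | SE, change | SE, adjusted | Power, change | Power, adjusted |
|---|---|---|---|---|
| 0.3 | 2.94 | 2.37 | 66% | 84% |
| 0.5 | 2.48 | 2.15 | 80% | 90% |
| 0.7 | 1.92 | 1.77 | 95% | 97.5% |

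**Percent change.** In a simulation with k = 1 (3,000 runs, 105 per arm, assumed baseline mean 80, values below 30 removed), power at r = 0.3 / 0.5 / 0.7 was 60 / 76 / 94% for percent change, 66 / 79 / 95% for absolute change and 83 / 89 / 97% for ANCOVA.

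**Baseline imbalance.** If the arms differ by δ at baseline, the expected difference in change shifts by (r/k − 1) · δ. With baseline SD 18, one standard error of imbalance is 18 · √(2/105) = 2.48. At k = 1 and r = 0.5 the shift is −0.5 · 2.48 = −1.24 mL/min/1.73m².

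**The case against.** The strongest reply is that nothing depends on these tests. The SAP calls them exploratory, the single confirmatory hypothesis is already baseline-adjusted, and under randomization a t-test on change is valid and unbiased on average. All of that stands, and it limits the point to efficiency.

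A reader might infer more, in four ways that the documents do not support:

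- **That the secondary objective is tested throughout without adjustment.** The objective names Months 6 and 12, and both have an ANCOVA contrast. SAP 2.5.2 also promises results for each time point. However, the renal parameters listed in SAP 2.5.1 omit MDRD-4, and only Month 6 is expressly said to include it. The remaining visits are therefore not clearly covered.
- **That the Visit 2 baseline is unstable.** No section says so. Protocol section 11 mentions short-term MMF use "to allow a slow increase in the tacrolimus level while renal function recovers", but as general practice and not as a description of Visit 2 eGFR here. SAP 2.3.5 assumes a fairly stable eGFR in the control arm. An unstable baseline would affect the size of the loss, not its direction.
- **That published intervals will be too wide.** No intervals are planned for these t-tests.
- **That the loss is large.** Only unfavourable values of r and k give that. Entry requires eGFR above 30, which truncates baseline and makes k below 1 plausible. Days 8 and 15 lie close to baseline, so a high r is plausible there.

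Two further objections stand. The t-test variable is inferred, not stated. And the t-tests are specified in the protocol, so demoting them is a departure that must be recorded.

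**Conclusion.** The point holds as a minor efficiency improvement. At Days 8 and 15 and Months 1, 3 and 9, the only clearly planned between-arm comparison of MDRD-4 eGFR is, on the natural reading, an unadjusted t-test on change. It cannot be more precise than the adjusted contrast from a model the SAP already fits, and it carries chance baseline imbalance whenever the slope on baseline is not 1.

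The direction follows from algebra. The size rests on an assumed baseline SD and correlation: an SE excess of about 1% (k = 0.8, r = 0.7), 8% to 24% (k = 1, r = 0.7 to 0.3), and about 53% (k = 1.33, r = 0.2). The primary Month 12 test, the Month 6 analysis and the sample size are untouched.

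**What to change.** In SAP 2.3.6, present the treatment contrast with 95% CI from the planned MMRM at every post-baseline visit, not only Month 12, and name it as the between-arm comparison for the eGFR course. Keep the tables of absolute and percent change, and any protocol-specified t-tests, as descriptive only. Record the change in SAP section 4.

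The code in SAP 5.5.2 has no LSMEANS or ESTIMATE statement, so one is needed even for Month 12, and asking for all visits adds almost nothing. The arm is called treatment in the CLASS statement and tgplc in the model, and the REPEATED statement uses time where CLASS lists visit; these names need aligning first.

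The cost is a little extra output and one documented departure from the protocol. No new data are needed.
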